3.1 Overview and Rationale of Intensity-Modulated Radiation Therapy (IMRT)

In contrast to the 3-5 beams used in conventional 3D techniques, multi-beam IMRT is an advanced method of delivering radiation that utilizes multiple (8-12) beams spread in an arc over the chest wall, where each beam delivers multiple intensity levels rather than one uniform intensity level to the target. This is achieved by changing the beam aperture during the —beam-on— time with dynamic multileaf collimators. Each beam delivers a different dose to the different parts of the target. The normal surrounding tissue is constrained such that high doses of radiation do not exceed the —limits— set on the normal critical organs. Multi-beam IMRT results in a homogeneous dosimetric plan to the target by eliminating high and low dose regions commonly seen in the junction region between the tangent beams and the anterior oblique beam of 3D-techniques, as well as within the implants.

Previous success has been demonstrated utilizing multi-beam IMRT for locally advanced breast cancer patients in a recently conducted departmental protocol, IRB #10-025 (Pilot Study of Multi-Beam Intensity-Modulated Radiation Therapy for Node-Positive Breast Cancer Patients Requiring Treatment of the Internal Mammary Lymph Nodes). This protocol closed in December 2012 after reaching its

target accrual goal of 116 patients within 30 months of initiation. Sixty percent of the study population consisted of patients with implant reconstructions. All patients were treated with a dosimetrically acceptable plan, thus meeting the criteria for feasibility. The rate of radiation pneumonitis in the entire cohort was 3.5%. Given the safety and the dosimetric advantages offered by this multi-beam, we continue to selectively treat patients with implant reconstructions requiring comprehensive PMRT with this technique.

By delivering a more homogeneous dose to the implant compared to conventional RT techniques, we hypothesize that multi-beam IMRT can reduce complications leading to implant failure and improve cosmesis in breast cancer patients with implant reconstructions requiring PMRT.

3.2 Overview and Rationale of Exploratory Objectives

3.2.1 $^{13}\text{N-NH}_3$ PET Scans to Estimate Cardiac Dose in Patients Treated with IMRT

Although it has been shown that IMRT limits the high dose delivered to the heart, the trade-off is that, compared to conventional radiation techniques, a higher volume of low dose is delivered to the thorax and heart. In order to quantify the low dose delivered to the heart with IMRT, the study will assess the patients with dynamic PET imaging that are obtained at the time of radiation simulation. Compared to other cardiac imaging modalities, PET has been shown to have improved performance attributable to the better spatial resolution and fewer image artifacts. Moreover, myocardial perfusion imaging with PET results in a lower radiation exposure to patients, on the order of a 20-25% reduction for $^{13}\text{N-NH}_3$ when compared to the commonly used Tc99m tracers (sestamibi and tetrofosmin). However, the feasibility of performing $^{13}\text{N-NH}_3$ cardiac PET scans within the RT simulation session has never been shown. The ability to perform the cardiac PET scans on patients in the radiation treatment position would allow optimal co-registration of the PET images with the CT images obtained from simulation. Accurate co-registration of the images at the time of simulation would subsequently enable accurate quantification of the radiation dose delivered to the heart from IMRT.

3.2.2 Assessing the Effect of IMRT on Early Subclinical Cardiotoxicity in Breast Cancer Patients

External beam radiation has been shown to cause chronic impairment of endothelium-dependent vasodilatation in humans *in vivo*, specific to arteries that received radiation [28]. Post-radiation cascade consists of loss of endothelial cells and increase in inflammatory response, which lead to micro- and macrovascular damage. Endothelial cell dysfunction is the initial and key insult in radiation-induced heart disease and is an important component of premature atherogenesis. The development of plaque formation from atherosclerosis leading to a cardiac event is a long process. Identification of early surrogate endpoints for the development of long-term cardiac morbidity after breast RT is therefore warranted. However, sensitive and reliable metrics for assessing early subclinical cardiotoxicity in patients treated with radiation are lacking.

[figure not shown]

Figure 3: Cardiopulmonary function is assessed by multiple organ systems

3.2.2.1 Strain Echocardiogram

Developments in echocardiographic imaging, such as speckle tracking strain echocardiography, have permitted a more accurate assessment of regional myocardial function. Speckle tracking echocardiography-derived strain imaging is a novel imaging modality that measures myocardial deformation and provides a more sensitive and quantitative assessment of cardiac contractile function than conventional 2D echocardiographic indices [29]. Strain echocardiogram is a highly reproducible and objective measurement that is superior to measures such as ejection fraction or fractional shortening in the detection of early subclinical myocardial dysfunction and has been shown to be useful in the early diagnosis of trastuzumab- associated cardiotoxicity [30,31]. An expert consensus statement from the American Society of Echocardiography in 2014 has recommended the inclusion of strain imaging for the evaluation of patients in preparation for, during, and after cancer therapy [32]. A pilot study in 30 breast cancer patients demonstrated the feasibility of strain echocardiography in evaluating early RT-induced cardiac changes, however this study was limited by older techniques that are currently not used in the United States [33].

3.2.2.2 Flow-Mediated Dilatation (FMD) Measurements via Ultrasound of the Brachial Artery

Endothelial dysfunction can also be measured by a process called flow-mediated dilatation (FMD), which describes the manner in which the endothelium responds to vasculature sheer stress [34]. Invasive methods of measuring endothelial dysfunction include sympathetic activation by cold pressor resting, dilator response to increased blood flow and dilatation in response to nitroglycerin. Each of these methods has been shown to be an independent predictor of poor prognosis, even after adjustment for traditional cardiovascular risk factors and the presence of atherosclerosis itself. A non-invasive and reliable method of studying FMD has been described by Celermajer and colleagues, in which flow is increased through the brachial artery by inducing post-ischemic dilatation in the downstream vascular bed of the distal forearm [35]. A cuff placed around the proximal forearm was inflated to higher than systolic pressure and produced ischemia in the distal vascular bed. After the

release of the cuff pressure, a sudden increase of blood flow into the dilated vascular bed occurred. The resulting increase in sheer stress in the upstream conduit artery causes dilatation of the brachial artery, which was measured by an ultrasound device, with dilatation reflecting increase in arterial endothelial nitrous oxide release [36]. This method is non-invasive, repeatable and reproducible, but requires specialized training to perform the ultrasound, which has limited broader utilization. Certified exercise physiologists within the MSK Cardio-Oncology Research Program (under the direction of [name]) will perform these measurements.

3.2.2.3 Cardiopulmonary Exercise Testing/VO₂ peak Measurements

It is possible that cardiac imaging tests and flow-mediated dilatation may be unsensitive predictors of cardiotoxicity. Cardiovascular reserve, as measured by cardiopulmonary exercise testing (CPET), is considered the gold standard assessment of exercise capacity and provides assessment of peak oxygen consumption (VO₂ peak)[37]. [name] and his team have had over 10 years experience of investigating the efficacy of supervised exercise training trials in patients with cancer across the entire cancer survivorship continuum, including breast cancer patients. The information gathered by this exploratory objective will be important in understanding to what extent IMRT reduces cardiovascular reserve, and the extent to which IMRT may impact the recovery of cardiovascular reserve in the sub-acute setting after treatment.

3.2.2.4 Cardiac Biomarkers

Cardiac biomarkers, particularly troponins, also have the potential to identify patients at risk for cardiotoxicity during early pre-clinical stages. Elevation of serum cardiac troponin levels in asymptomatic patients after administration of anthracycline-based chemotherapy have been shown to predict subsequent deterioration of myocardial function [38]. In contrast, very limited data exists on the role of cardiovascular biomarkers in the detection of RT-induced cardiotoxicity. The levels of multiple cardiovascular biomarkers that are mechanistically relevant to cardiotoxicity will be examined in this protocol. NT-proBNP is an established biomarker for the diagnosis and prognosis of heart failure, and high sensitivity troponin-I (hsTnI) has been used to measure myocardial injury and to predict incident LV dysfunction among patients receiving chemotherapy [39]. Endothelin is involved with the vascular regulatory system and may have prognostic value in patients with heart failure [40]. Matrix metalloproteinase (MMP)-2 and 9 and their tissue inhibitors (TIMP) play a major role in left ventricular remodeling and the development of heart failure[41-43]. Inflammatory markers, including high-sensitivity C-reactive protein (hsCRP), interleukin (IL)-6, and tumor necrosis factor-alpha (TNF- α) are elevated in patients with heart failure as well as patients with asymptomatic left ventricular dysfunction, raising the possibility that inflammation may contribute directly in the pathogenesis of heart failure [44,45]. This study will explore the utility of multiple novel biomarkers to identify patients at risk for cardiotoxicity following chemotherapy and radiation therapy to the chest wall and regional lymph nodes.

3.2.3 Assessing the Effect of IMRT on Quality of Life in Breast Cancer Patients

Although radiation to the chest wall and lymph nodes for breast cancer is a well-tolerated treatment, the effect of radiation on functional status of patients has not been well quantified. Fatigue levels and quality of life may also be important indicators of cardiopulmonary dysfunction in patients who have received radiation therapy.

4.0 OVERVIEW OF STUDY DESIGN/INTERVENTION

4.1 Design

This is a Phase II trial examining the efficacy of multi-beam IMRT in reducing implant failure rates (primary endpoint), as well as the secondary endpoints of cosmesis, incidence of capsular contracture and minor revisional surgeries, and the correlation of MRI changes with clinical assessments of capsular contracture in breast cancer patients with implant reconstruction receiving PMRT. We will test the hypothesis that the 2-year probability of implant failure will be reduced by a relative 30% or greater compared to our aforementioned published experience of implant failure following PMRT with conventional radiation techniques.

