MSKCC's institutional experience of 151 patients who received PMRT following expander/implant reconstruction, the 7-year permanent implant failure rate was 29%, with the majority of events occurring within 1-2 years after radiation. Infection was a major cause of implant removal, whereas capsular contracture was the most dominant cause for implant replacement. This data is consistent with multiple reports in the literature where capsular contracture remains the most significant long-term risk following irradiation of implant reconstructions, even with improvements in implant technology and surgical techniques over the past decade [13-16]. Recently, additional data from MSKCC has been published by Cordeiro et al [51], which demonstrated that implant failure rate was higher when patients were irradiated to the tissue expander vs. the permanent implant, thereby demonstrating the significance of the timing of radiation therapy relative to reconstruction when assessing reconstructive outcomes.

Existing Methods for Assessing Capsular Contracture and Cosmesis After Implant Reconstruction

To date, the standard tool for estimating the presence and severity of capsular contracture is the Baker scale, which was developed in 1979 and consists of a standardized 4-point scale that integrates the appearance, texture and tenderness of the examined breast. Studies have shown that the Baker score can be subjective and lead to inter-rater (and possible intra-rater) variability [5].

Methods such as measurement of pressures inside the breast pocket using tonometry or other techniques have been attempted. However, none of these tools have gained widespread acceptance. Subsequently, there is difficulty in assessing the extent of capsular contracture, resulting in a wide range of capsular contracture rates reported in the literature [17]. The lack of an objective way to measure capsular contracture has hindered efforts to establish standardized treatment guidelines for capsular contracture.

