We have published that exchanging the expander to the implant prior to the start of radiation therapy is associated with excellent long-term clinical outcomes and acceptable complication rates in patients who received adjuvant chemotherapy [20]. Thus, in these patients (represented in Group 1), our institutional policy is to initiate radiation after the expander has been exchanged for the permanent implant.

In approximately 30-40% of locally advanced breast cancer cases, upfront surgical down-staging of the tumor with systemic therapy is required and therefore these patients received neoadjuvant chemotherapy, followed by mastectomy with immediate tissue expander placement (represented in Group 2). In such patients, there is often inadequate time to complete expansion, perform exchange and achieve adequate tissue healing prior to initiating radiation. Hence, the exchange procedure for a permanent implant is delayed until approximately 4-8 months after the end of radiation, when the tissues have recovered from radiation injury as determined by the treating plastic surgeon. Radiation is subsequently delivered to the tissue expander and regional lymph nodes.

Over the past several years, over 50% of locally advanced breast cancer patients who receive postmastectomy radiation therapy at MSKCC are treated with comprehensive radiation therapy to the chest wall and regional lymph nodes [departmental statistics]. Regional lymph node irradiation includes the axillary, supraclavicular and internal mammary nodes. PMRT therapy has been shown to positively impact disease free survival and overall survival [21-24]. The most recent meta-analysis from the Early Breast Cancer Trialists' Collaborative Group (EBCTCG) showed that adjuvant radiation therapy improved 15-year breast cancer mortality in node positive patients treated with mastectomy and lymph node dissection[1]. Twenty-four of the 25 PMRT studies included in the EBCTCG meta-analysis performed Internal Mammary Node (IMN) irradiation, suggesting that the benefits of PMRT may be

related to their treatment [1]. Interest in IMN irradiation has recently been fueled by the results from the National Cancer Institute of Canada (NCIC) MA-20 trial demonstrating improved distant disease-free survival and a favorable trend in overall survival in breast-conservation patients receiving comprehensive regional node treatment[25].

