6.0 CRITERIA FOR SUBJECT ELIGIBILITY

6.1 Subject Inclusion Criteria

1. Females who are ≥ 18 years of age with a life expectancy estimated to be at least 2 years

2. Histologically-confirmed invasive breast cancer by MSKCC
3. Eastern Cooperative Oncology Group (ECOG) performance status of 0 or 1
4. Status post mastectomy with surgical assessment of axillary nodes
5. Immediate reconstruction with tissue expander (Group 2) or permanent implant (Group 1) prior to RT performed at MSKCC
6. If PMRT is recommended, the treatment fields will include the axillary, supraclavicular, and internal mammary nodes

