14.0 BIOSTATISTICS

14.1 Statistical Plan for Assessment

14.1.1 Implant Failure

The primary objective of this study is to assess for the reduction of implant failure associated with multi-beam IMRT, compared to our published historical implant failure rates associated with conventional radiation techniques. The primary endpoint is incidence of implant failure by the end of the study period (24 months post-IMRT for Group 1, and 30 months post-IMRT for Group 2).

Our published data and recent findings in the literature suggested that the implant failure rate (implants that are removed or replaced by another reconstruction) was 20% at 24 months post-IMRT for group 1 [20] and 30% at 30 months post-IMRT for group 2 [51]. Assuming that 1/3 of the patients we will enroll are going to be in group 1 and the remaining 2/3 will be in group 2, we set up the hypotheses that an implant failure rate of 26% or more is considered unacceptable while 16% or less is considered acceptable. Since the endpoint cannot be measured until 2 years after the treatment, we will utilize a one-stage design. We will test the hypothesis using a binomial test based on a cohort of 100 patients. We insist that at minimum 34 of them will be enrolled in group 1 and at minimum 66 will be in group 2, and we will combine them for the primary objective. We will claim that multi-beam IMRT significantly reduces the implant failure rate if no more than 20 patients have an implant failure after IMRT within 24 months of the treatment for patients in group 1 or within 30 months after IMRT in group 2. For this decision rule, we have a type I error (i.e., claiming multi-beam IMRT promising while it is not) rate less than 0.10 and a type II error (i.e., claiming multi-beam IMRT not promising while it actually is) rate less than 0.15.

Because there is no reason why local control or lung or other toxicities would be impacted secondary to treatment with multi-beam IMRT instead of conventional treatment, an early stopping rule in order to detect early recurrences was not deemed necessary.

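### The primary claim is worded as a significant reduction against conventional radiation, but its stated type I error holds only if the historical 26% failure rate is exactly right

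*Combined protocol and SAP*

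**What the plan says.** Section 4.1 frames the hypothesis as a relative reduction "compared to our aforementioned published experience of implant failure following PMRT with conventional radiation techniques", and section 14.1.1 repeats that comparison with the centre's own history as the primary objective.

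Section 14.1.1 then fixes the benchmark. It begins "Our published data and recent findings in the literature suggested that the implant failure rate" and says that this rate "was 20% at 24 months post-IMRT for group 1 [20] and 30% at 30 months post-IMRT for group 2 [51". (The rates carry a post-IMRT label, but the section presents them as the conventional-technique history.) With about one third of patients in group 1 and two thirds in group 2, it sets the thresholds: "an implant failure rate of 26% or more is considered unacceptable while 16% or less is considered acceptable". The analysis is a one-stage binomial test on 100 patients, at least 34 in group 1 and at least 66 in group 2, combined.

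The conclusion is worded as follows: "We will claim that multi-beam IMRT significantly reduces the implant failure rate if no more than 20 patients have an implant failure". The stated errors are below 0.10 (type I) and below 0.15 (type II).

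No interval, standard error, series size or sensitivity analysis accompanies the 20% and 30%. There is no randomization (section 15.2), and the unirradiated group 2B is kept out of the primary analysis (section 14.1.4). The only historical series with a stated size is in section 3.0, "MSKCC's institutional experience of 151 patients who received PMRT following expander/implant reconstruction", and it is reported there with a 7-year failure rate of 29%.

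**The concern.** The claim compares two treatments, but the test compares one sample with a constant. An error rate calculated at a fixed 26% answers this question: if the true no-effect rate in these patients is 26%, how often would the rule be met? It does not answer the question that the wording raises, which is how often IMRT would be declared a significant improvement when it is no better than conventional radiation.

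The two questions have the same answer only if 26% is the true conventional rate. The figure comes from finite retrospective experience, so it has sampling error, and the rule is steep in this region. If the true conventional rate were two points lower, an ineffective technique would pass about one time in five, and the result would still be reported as significant.

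**Working it through.** **Inputs.** From section 14.1.1: n = 100, a claim if failures X ≤ 20, p0 = 0.26, p1 = 0.16, historical rates 20% (group 1) and 30% (group 2), split 34/66. From section 3.0: 151, the only historical series size given.

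**Step 1: the plan's own figures.** Exact binomial, P(X ≤ 20) = Σ(k = 0 to 20) C(100,k) p^k (1−p)^(100−k).

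- Type I at p = 0.26: 0.1027. The stated bound of 0.10 is narrowly missed.
- Type II at p = 0.16: P(X ≥ 21) = 0.112, which agrees with the stated bound of 0.15.
- The unrounded benchmark is (34 × 20% + 66 × 30%)/100 = 26.6%. With 34 patients at 20% and 66 at 30%, the type I error is 0.080.
- The normal approximation without continuity correction gives (20 − 26)/√(100 × 0.26 × 0.74) = −1.37, or 0.086.

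So a value below 0.10 follows from the unrounded mix or from that approximation, but not from the binomial test at 26%.

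**Step 2: sensitivity to the benchmark.** If IMRT has no effect, the trial's failure rate equals the true conventional rate:

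| True conventional rate | P(claim) |
|---|---|
| 22% | 0.366 |
| 24% | 0.208 |
| 26% | 0.103 |
| 28% | 0.044 |

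**Step 3: averaging over sampling error, one series.** Assume the whole 26% comes from one series of m patients and average P(X ≤ 20) over p ~ Beta(0.26m, 0.74m). For m = 151 the standard error is √(0.26 × 0.74/151) = 0.036, giving a 95% range of about 19% to 33%.

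- m = 100: 0.19
- m = 151: 0.17
- m = 300: 0.14

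**Step 4: the same with two sources.** Section 14.1.1 cites a separate source for each group. Take group 1 as Beta centred at 20% (size m1) with 34 trial patients, and group 2 as Beta centred at 30% (size m2) with 66. With no benchmark error this gives 0.080, as in step 1.

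- (m1, m2) = (151, 50): 0.16
- (151, 100): 0.13
- (151, 151): 0.12
- (151, 200): 0.11
- (300, 300): 0.098

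Every series size in steps 3 and 4 is an assumption. That includes 151, because the documents do not tie that series to the 20% at 24 months or to the pooled 26%.

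**Step 5: a result that just passes.** Compare 20/100 with 39/151 (0.26 × 151 = 39.3, rounded). The pooled z is −1.07, one-sided p = 0.14; Fisher's exact one-sided p = 0.18. Against a comparator of that size, a bare pass would not reach 0.10.

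**The case against.** A fixed benchmark is ordinary in a single-arm phase II trial. Section 14.1.1 states its thresholds openly and defines both errors in terms of calling IMRT promising, which is a screening conclusion. The benchmark is built by reconstruction sequence, so it has some case-mix alignment. Rounding 26.6% down to 26% is conservative. In the two-source calculation with large series, the averaged error is 0.098, inside the stated bound. All of this stands. It is why the rule and the sample size need not change. It does not rescue the wording of a pass, which goes beyond screening, or the absence of any allowance for error in the benchmark.

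A reader might infer something stronger: that the historical patients had a different field mix, so the false-claim rate is well above 0.10. Section 6.1 requires that, where radiation is recommended, "the treatment fields will include the axillary, supraclavicular, and internal mammary nodes", while section 3.0 says that "over 50% of locally advanced breast cancer patients who receive postmastectomy radiation therapy at MSKCC are treated with comprehensive radiation therapy". But the second statement describes recent departmental practice, not the series behind the 20% and 30%, whose fields are reported nowhere. The direction is also open. If fuller fields raise implant failure, the no-effect rate in this trial lies above 26% and the false-claim chance falls, to 0.044 at 28%.

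The accrual share is no evidence of selection bias either. Enrolling 130 patients over three to four years from 200 to 300 eligible a year takes between 130/4/300 = 11% and 130/3/200 = 22%. Enrolling a fraction of eligible patients is normal and says nothing about their failure risk.

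**Conclusion.** The concern holds as a matter of what the test can support. The type I error is conditional on a true conventional rate of 26% and is 0.103 there by the stated test. Carrying sampling error in the historical rates gives roughly 0.10 to 0.19: about 0.10 to 0.16 with two sources and 0.14 to 0.19 with a single series of 100 to 300 patients. No single figure can be fixed, because the series sizes are not stated. The documents do not establish that the error is well above 0.10 or that the historical fields differed. Bias from fields or case mix could act in either direction and cannot be sized from the documents. The change is worth making because the planned conclusion claims a significant reduction against conventional radiation that a test against a constant does not show.

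**What to change.** Keep the 20-of-100 rule and the sample size. In section 14.1.1:

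- **Error rate.** Replace the bound of 0.10 with 0.103, say that it is conditional on a true conventional rate of 26%, and print the claim probability at 22%, 24%, 26% and 28%.
- **Wording of a pass.** Report *failure rate below the 26% benchmark* in place of a significant reduction.
- **One supportive estimate.** Give the difference in failure proportion from the historical rates, stratified by group (24 months for group 1, 30 months for group 2), with an interval that carries the sampling error of both samples. Use the published counts if patient-level data are unavailable. Restrict to comprehensive-field patients only if fields were recorded.

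Tightening the rule is not recommended. If one series of 151 carried the whole 26%, a cut-off of 18 would bring the averaged error to 0.087, but power at 16% would fall from 0.888 to 0.758.

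The cost is SAP text and one additional analysis, a slightly less favourable stated error rate, and a wider supportive interval. The documents do not show whether patient-level historical data or field records exist, so the field-restricted version may not be possible.
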